The training consists of computerised working memory updating tasks in which trial accuracy and response time are recorded. All 8 WMU interventions will be delivered by the PhD researcher on a group basis (group size N = 2 – 6). Two computerised WMU tasks will be trained based on the study conducted by [name] on healthy adults (Flegal et al., 2019). These tasks will be delivered via two modalities: (1) a visuospatial WMU task, i.e. Matrix Updating (MU) and (2) a verbal WMU task, i.e. Keep Track (KT). MU requires updating the location of multiple dots within a 4 x 4 matrix (Chen and Li, 2007) while KT requires updating the identity of the most recently studied words in multiple semantic categories (Yntema, 1963). For both training tasks, level of difficulty can be modulated by increasing or decreasing the update level, i.e., the number of updates on each trial. For AT participants, difficulty of the training tasks is progressively increased in response to task performance, in order to adaptively increase environmental demands. For NA participants, however, task difficulty is fixed at a relatively low level across all sessions. Training of the MU task lasts between 25-30 minutes while the KT training lasts between 20-25 minutes. The WMU training sessions will last between one hour to one hour and fifteen minutes taking into consideration time to provide instructions and practice.

ix. Post-intervention Feedback

After the end of the intervention all participants will have the opportunity to rate the perceived usefulness and experience of the interventions including any adverse effects using Likert scales (for further details please see the feedback form). This information will be used to guide the possible development of a future full-scale trial. This will be carried together with the immediate follow-up session after the end of the intervention (i.e. visit 12) by the PhD researcher.

x. Outline of Study Visits

Visit 1: Baseline Neuropsychological and Functional Assessment and Introductory GMT session

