The WMU training sessions will take place remotely. A computer with Windows Vista/7/8/10 is required to run the WMU training tasks using the Presentation software by Neurobehavioural Systems specifically designed for secure remote management of stimulus delivery in experimental research <https://www.neurobs.com/>. If participants have no personal computer access, then the research team is able to provide the necessary equipment for the duration of the intervention depending on numbers and availability. The PhD researcher will be offering individual practice sessions and detailed step-by-step guidance for using the presentation software prior to starting the training sessions. The training tasks, session duration and content will remain unchanged as originally planned. All devices will be disinfected before given to a new participant using alcohol based sanitising products, i.e. 60-80% alcohol, as recommended per NHS guidelines <https://coronavirusexplained.ukri.org/en/article/pub0006/>

- Scanning sessions – Visits 2 and 11

The scanning sessions at CRIF will adhere to COVID-19 related NHS regulations and guidelines. Consequently, the sessions will be conducted as originally planned while ensuring the necessary precautions are taken to protect participant's health and safety. If participants feel uncomfortable taking part in the scanning sessions for reasons relating to COVID-19, then those people will only participate in the intervention component of the study.

- NHS-approved software

The online version of the intervention will be conducted using NHS approved software, such as Attend anywhere, Microsoft Teams and National Video Conferencing Service (NVCS) Cisco Meeting Server (CMS) which have already been adopted by the NHS to run their service remotely, i.e. one to one sessions and group meetings. These are ideal for sharing content, e.g. GMT module slides, for taking part in a group chat as well as support larger size group meetings effectively. The softwares will be accessed remotely through NHS networks to ensure data security and protection.

5. Randomisation and Bias prevention

Stratified randomisation in conjunction with permuted block random allocation will be used to allocate participants to one of two study groups of equal size. The sample will be stratified

by the following factor: aetiology of brain injury (two strata, i.e. TBI or stroke. Participants will be blinded to study allocation.

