The sample will be randomised by [name], a member of the PhD researcher's supervisory team. [name] is a neuroscience researcher with an expertise in fMRI methodology and thus she is less likely to come in direct contact with the participants through the clinical domain. The randomisation procedure will be conducted in a computerised manner. A code for randomisation will be created using Matlab programming software. Two databases will be created: 1. a patient's database that lists basic information such as participant ID, recruitment site, age, aetiology of brain injury and 2. a "randomisation" database that holds data on which participants have been registered and their treatment allocation. The participants' database will be password protected and accessed only by [name]. The PhD researcher will have no way of knowing which participant is allocated into which intervention arm prior to the individual starting the trial or change it afterwards. For the purposes of the present project stratified randomisation with blocking will be used and thus several participants will be randomised at once. Alternatively, if [name] is unable to perform the randomisation for any reason [name] will conduct the procedure instead.

1. Sample size

Thirty-two participants will be randomised (16 per group) to estimate recruitment, adherence and retention rates, and the variance of outcome measures. The sample size was based upon what could be feasibly expected to be recruited as part of a small-scale PhD feasibility research study whilst accounting for eligibility restrictions especially in regards to MRI contraindications as well as the duration of the study. i.e. committing to the study for 12 weeks. Given that one of the primary aims is examining feasibility and acceptability of the novel intervention, the study is not designed to be powered to detect differences in outcomes between the two groups.

2. Neuroradiologist Report of Structural Scans

[name] is the collaborator Neuro-radiologist in this study. She will review structural brain images acquired with the following sequences: 1. T1-weighted, 2. Axial T2-weighted, 3. Axial T2-weighted FLAIR, and 4. a haemosiderin sensitive sequence (e.g., gradient-echo or susceptibility-weighted). These scans will be transferred to NHS PACS in order to be linked to each participant's medical record. This way [name] will be able to produce a comprehensive report in CRIS for each participant to:

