Quantitative behavioural data will be analysed using SPSS 21 software or equivalent. Data on recruitment, adherence and retention rates will be summarised as percentages with 95% confidence interval (CI). Baseline characteristics of the sample will be presented using descriptive statistics. Measures of cognition (overall and domain specific composite scores) and psychological and functional constructs will be summarised by group and overall with 95% CI, and analysed using correlational analyses and t-tests or their non-parametric equivalents to estimate effect sizes (ES). The estimated ES, Cohen's d (Sullivan & Feinn, 2012), will be calculated using linear regressing adjusted for baseline and factors. The sample means, SD and change scores on these outcome measures will form the basis of sample size calculations for a further full-scale study, if indicated.

fMRI BOLD responses will be analysed using the general linear model implemented in SPM12 developed at the Wellcome Center for Human Neuroimaging, UCL (www.fil.ion.ucl.ac.uk/spm). Data preprocessing will include each participant's functional images being realigned using a six-parameter rigid body transformation and coregistered to their anatomical image. Covariates of interest will be constructed by convolving vectors of predicted neural activity with a canonical hemodynamic response function. To account for residual variance because of head movement, motion parameters will be estimated at the realignment stage of pre-processing and motion spikes will be identified using the ArtRepair toolbox (cbsr.stanford.edu/tools/human-brain-project/artrepair-software.html) and included in each model as covariates of no interest. For group analysis, functional images will be normalised to MNI (Montreal Neurological Institute) space using affine and nonlinear transformations, and spatially smoothed.

5. Data Storage & Sharing

All sensitive information such as participants' names, addresses, phone numbers etc will remain on NHS systems. All electronic anonymised data will be stored on secure University

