of Glasgow networked drives accessed via password-protected university (laptop) computers to ensure that the data is automatically backed-up. All participants will be assigned a study ID and all electronic data will be anonymised using this unique identification number. Physical data will be stored in locked filing cabinets in locked offices on University of Glasgow premises. The index of ID codes and identities will be stored separately from the study data. A secure University network drive will be used for the purpose of sharing raw data between the PhD researcher and investigators. If the data were to be shared, it would be completely anonymous (i.e. the link between participant name and study ID would be broken and a random ID number would be given instead). Please see **further details on the data management plan document**.

6. PhD student training

The PhD student, [name], has attended the following training opportunities to ensure she can produce high quality research, perform the Goal Management Intervention and conduct the fMRI scanning sessions together with the qualified radiographer at the CRIF, QEUH.

1. **Research Data Management** (October 2018), University of Glasgow
2. **Ethical Approval for People Working with Human Subjects** (November 2018), University of Glasgow
3. **Good Clinical Practice** (November 2018), NHS Greater Glasgow and Clyde
4. **MRI Safety Training**, (November 2018), University of Glasgow
5. **Goal Management Training** online attendance (December 2018), organised by Baycrest, University of Toronto, <http://goalmanagementtraining.weebly.com/>
6. **Applied Statistics for Postgraduate Students** (January 2019), University of Glasgow
7. **Writing a Data Management Plan** (May 2019), University of Glasgow
8. **Statistical Parametric Mapping (SPM) Course**, Wellcome Centre for Human Neuroimaging (May 2019), University College London
9. **Visceral Mind Neuroanatomy Course**, (September 2019), University of Bangor

7. Dissemination plan

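### Image processing is not masked and has no written rule for unusable runs, so decisions behind the adaptive (AT) versus non-adaptive (NA) fMRI comparison could be made with the arm known

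*Combined protocol and SAP*

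**What the plan says.** **Masking and allocation (section 5, Randomisation and Bias prevention).** The only masking statement is "Participants will be blinded to study allocation". Randomisation is done by "a member of the PhD researcher's supervisory team", who "is a neuroscience researcher with an expertise in fMRI methodology and thus she is less likely to come in direct contact with the participants". A second person may randomise instead. One database "holds data on which participants have been registered and their treatment allocation". The stated access limit belongs to the other database: "The participants' database will be password protected and accessed only by" one person, whose name is removed. The PhD researcher is kept from knowing the arm only until the individual starts the trial.

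**Delivery and scanning (sections 4.viii and 4.x).** "All 8 WMU interventions will be delivered by the PhD researcher on a group basis". Task difficulty rises with performance in AT and stays fixed and low in NA. If the sessions are done at home, the performance files go to the PhD researcher. The same researcher conducts both scanning sessions with a radiographer.

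**Image analysis (Neuroradiologist Report of Structural Scans; Statistical methods; PhD student training).** Lesion location, size and number are to inform coregistration and spatial normalisation. The pipeline is SPM12 with six-parameter realignment, MNI normalisation and smoothing, and "motion spikes will be identified using the ArtRepair toolbox", with the spikes entered as covariates of no interest. The PhD researcher has attended an SPM course.

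**Outcome (section 3.ii).** Pre- to post-training change in task-related brain activity, compared by training condition, is a secondary outcome.

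**The concern.** The reason given for the randomiser's independence is low clinical contact. That protects enrolment and patient handling. It does nothing for the imaging outcome, where the risk lies in how scans are processed and which are judged usable. Two people are described with relevant fMRI skills, the randomiser and the PhD researcher. The first produces the allocations and the second sees them in practice. If either processes the images, nothing in the plan keeps the arm out of view.

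At stake is the second research question, whether the combined treatment produces neural change detectable by fMRI. With so few participants per arm, a handful of usability or lesion-handling decisions can matter, and a reader of the results could not rule out that the arm influenced them. The point concerns image processing only. Masking the Visit 12 assessor would not resolve it.

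**Working it through.** **1. Who can know the arm, and what each could influence**

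| Role | Knows the arm? | Link to the images |
|---|---|---|
| Participant | No (stated) | None |
| Randomiser, or the deputy | Yes, by doing the task | fMRI expertise stated for the main randomiser; analysis role not stated |
| PhD researcher | Yes, once WMU delivery starts | Helps run both scans; SPM course; analysis role not stated |
| Image analyst | Not stated | Not named |

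Access to the randomisation database is not described. Study IDs hide the name, not the arm.

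**2. Where discretion remains**

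- Lesion handling in coregistration and normalisation is specific to each participant.
- No motion cut-off, spike threshold or smoothing width is given.
- No rule says when a run or scan is unusable. The pipeline describes no exclusion step at all.
- Realignment is automated, and spikes are modelled as covariates, so flagging a spike does not by itself drop a scan.

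**3. Sample size**

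2 × 16 = 32, which agrees with the plan. The imaging comparison has at most 16 participants per arm, each scanned twice, and fewer if some take part without scanning under the COVID-19 provisions. The plan gives no alpha, power, effect size or SD. The approximate 95% half-width on d with 16 per arm is 1.96 × √(2/16) = 0.69.

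**4. Illustration of sensitivity (assumptions, not figures from the plan)**

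Assume 16 per arm, standard-normal change scores, no true difference, and a t-test at two-sided 5%. In each arm k participants are borderline. A borderline participant is kept only if above the arm mean in AT, or below it in NA. About half are kept, with mean about √(2/π) = 0.798 in the favoured direction, so approximately

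d ≈ 2 × (k/2 × 0.798) / (16 − k/2)

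| k per arm | Formula | Simulated mean d | Rejection favouring AT (nominal 2.5%) | Two-sided rejection (nominal 5%) |
|---|---|---|---|---|
| 1 | 2 × 0.399/15.5 = 0.05 | 0.05 | 3.2% | about 5% |
| 2 | 2 × 0.798/15 = 0.11 | 0.12 | 5.0% | 5.9% |
| 3 | 2 × 1.197/14.5 = 0.17 | 0.17 | 6.1% | 6.9% |
| 4 | 2 × 1.596/14 = 0.23 | 0.23 | 8.1% | 8.6% |

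Repeat runs agreed to within about 0.01 in d.

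The rule uses both the arm and the result. When borderline participants are dropped without regard to result, mean d is about 0.00 and two-sided rejection about 5% for k = 1 to 4. Other rules give other shifts. Dropping the 1, 2 or 3 least favourable participants in each arm gives d of 0.26, 0.53 or 0.81, but that is outright selection on results.

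**The case against.** The strongest case on the other side has four parts.

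*The plan never says that processing is unmasked.* True. The point rests on silence, and no role is assigned for image analysis. But the section on bias prevention says who is blinded, and stops at the participant.

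*The fMRI expert is not shown to hold the list or to analyse the scans.* This stands. A reader might infer that the allocation list sits with the person who will process the images. The documents do not support that: the one-person access rule is written for the participants' database, the name is removed, and a deputy may randomise. With names removed, other investigators may also have the skills. The PhD researcher's knowledge of the arm, however, is not in doubt.

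*Much of the pipeline leaves little room for choice.* This largely stands. Spikes become covariates, and smoothing reads as one step for the whole group. What remains is lesion handling, scan usability and settings not yet stated. A written rule would remove much of this discretion even without masking.

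*The simulated shift is not the effect of missing masking.* This stands. Knowing the arm alone gives no direction; the decision-maker must also have seen the results. Even then, a shift of 0.11 to 0.12 at k = 2 is small beside a half-width of 0.69, and two-sided error rises only from 5% to 5.9%. It would be wrong to read the table as a prediction of bias in this trial.

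**Conclusion.** The point holds as a gap in protection, not as evidence of bias. Only participants are masked, the PhD researcher necessarily learns the arm, and the plan leaves lesion-specific processing and scan usability without a rule and without masking. Whether the analyst will know the arm is not stated.

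The size of any bias is unknown. A shift in d of about 0.05 to 0.23 needs 1 to 4 borderline participants per arm and decisions made knowing both arm and result; both are assumptions. A reader might infer that unmasked processing by itself would create an AT–NA difference, or that the trial's main conclusions are at risk. Neither follows: exclusion unrelated to result leaves d at about zero, and the primary outcomes are feasibility, acceptability and fidelity. The study is also declared not powered for group differences. Because estimating effect sizes is a stated aim, a cheap safeguard is still worth adding for this secondary outcome.

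**What to change.** Add to the fMRI part of Statistical methods:

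1. Name the role that processes the images, and state who can open the randomisation database.
2. Before preprocessing, write down the motion cut-off, run-exclusion rule, smoothing width and lesion-handling rule.
3. An existing team member who does not analyse images replaces study IDs with random scan codes and keeps the key. The lesion information used in normalisation carries the same codes. The section on Data Storage & Sharing already foresees for shared data that "a random ID number would be given instead".
4. Complete and lock preprocessing, normalisation checks, first-level models and the list of excluded runs under these codes, with a date.
5. Merge the arm only for the group model. Until the lock, nobody with the allocation list takes part in decisions on uncoded files.

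The cost is a renaming script, a code list, a dated lock file and a short delay. No extra staff or scans are needed, and the sample size stays at 32. Masking will be imperfect where the analyst recognises a lesion, so the written rules in step 2 matter as much as the codes. The change must be made before processing starts, because masking cannot be restored afterwards.
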